This study is designed to determine whether SeraSeal is effective as a primary hemostatic agent, and safe in achieving hemostasis in surgical wounds or other emergent hemorrhagic episodes. The effectiveness will be determined by achieving hemostasis after application of the product. The safety will be determined by monitoring outcomes from application: recurrence of bleeding, infection, lack of healing, and presence of hypersensitivity reactions, e.g. pruritus, fever, rash, anaphylaxis.

Characteristics of SeraSeal

SeraSeal is a bovine protein-derived accelerator of hemostasis interacting with the intrinsic and extrinsic pathways. It is obtained from pathogen and prion free cows. SeraSeal can be provided as a solution, spray, foam, incorporated into an absorbable dressing or a non-absorbable removable dressing. Its active ingredients are Factors IIa, VIIa, IXa, and Xa.

Toxicity of SeraSeal

A total dosage level of SeraSeal over 13,000 IU/Kg (2.4 mg protein) in leporids and canines had no adverse effects^{24,25}. The total expected treatment levels to be used in this study is less than 1,000 IU/Kg, a thirteen fold lower level than the no toxic effect. Thus, drug related toxicity is not expected to be seen in this clinical study. Cell culture studies reveal that SeraSeal is not directly toxic for any cells tested.

5.6 Research Design and Methods: This clinical trial will be a non-randomized, unblinded study where SeraSeal will be used as a liquid, administered by a syringe (300 IU/0.1ml) or spray (210 IU/pump), and compared to standard surgical methods to control bleeding in historically known surgical cases taking more than 6 minutes to control all of the hemorrhages. The intent-to-treat patients will be placed into either the SeraSeal syringe treatment group, where bleeding from medium to large blood vessels may occur, or the SeraSeal spray treatment group, where only capillary to small blood vessels would be treated with the investigational product.

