Patients receiving treatment at Joaquin Albarran Hospital, Salvador Allende Hospital, and National Institute for Cardio-Vascular Surgery, will serve as study volunteers. Prior to enrollment in the study, an initial screening test and subsequent studies will take place, including: informed consent, collection and recording of subject demographic information, medical history, current medications, assessment of inclusion/exclusion criteria, physical examination, with blood draws for hematological assessment for bleeding and time to hemostasis. The location of the study wounds will be skin-skin. The study wound sites will involve bone and soft tissue.

The primary endpoint in this clinical trial is hemostasis. A Secondary endpoint is the number of surgical cases without a therapeutic break from SeraSeal to a standard surgical modality to control the bleeding. There are 10 designated surgical faculty members from General Surgery, Vascular, Obstetrics and Gynecology participating in this study, with a minimum of 10 surgical procedures being studied. All of the participating surgeons are highly skilled and have extensive expertise in their surgical specialty.

In this trial, the dosage level of SeraSeal vial is 300 IU/0.1ml and 210 IU/pump in the spray, with a maximum expected dosage of 10,000 IU, 20 times less than the pre-clinical toxicity studies. After 1-2 minutes, when hemostasis is achieved, the excess SeraSeal will either be removed through suction or absorption onto a surgical sponge. A time to hemostasis is measured from the time when the product is first applied to the wound, until no bleeding or oozing is observed from the wound. A nurse will use a stopwatch to record the time to hemostasis. SeraSeal will be used from the initial incision and through out the entire surgical procedure, and the time to hemostasis for each bleed will be measured, then totaled for the entire surgery. SeraSeal is expected to achieve a total hemostasis time under 5 minutes. Stopping criteria for treatment will be when hemostasis fails to be achieved after 3 applications for a particular wound, the collective time to hemostasis exceeds 5 minutes, the patient experiences a serious adverse event, or at the surgeons discretion. If this should happen, the patient will be switched over to standard surgical practices.

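### A case switched to standard methods before 5 minutes, chiefly at the surgeon's discretion or for a serious adverse event, can still count within the primary 5-minute criterion

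*Protocol*

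**What the plan says.** Protocol 5.6 names hemostasis as the primary endpoint. Section 5.2 sets the target: a summed hemostasis time below 5 minutes in 95% of cases. The sample-size paragraph in 7.2 rests on the same outcome.

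The clock is also fixed in 5.6. Each bleed is timed by this rule: "measured from the time when the product is first applied to the wound, until no bleeding or oozing is observed from the wound". The case total follows from a second rule: "the time to hemostasis for each bleed will be measured, then totaled for the entire surgery".

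Four stopping criteria follow. The first reads "Stopping criteria for treatment will be when hemostasis fails to be achieved after 3 applications for a particular wound". The second is that the summed time has passed 5 minutes. The last two are that "the patient experiences a serious adverse event, or at the surgeons discretion". The consequence is the same for all four: "If this should happen, the patient will be switched over to standard surgical practices". No outcome on the primary is assigned.

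Use of a standard method is captured separately. The secondary endpoint is the "number of surgical cases without a therapeutic break from SeraSeal to a standard surgical modality to control the bleeding". Section 7.2 lists time to hemostasis and therapeutic breaks side by side and does not combine them.

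Two other statements show what the primary is meant to measure. Section 5.1 has SeraSeal used from first incision to closing with no standard method brought in to stop bleeding. Section 5.5 says: "The effectiveness will be determined by achieving hemostasis after application of the product".

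**The concern.** The clock asks when the bleeding stopped. It does not ask what stopped it. If SeraSeal is abandoned on a bleed and a ligature ends it, the definition still yields a valid time for that bleed. If the case total stays under 5 minutes, the case satisfies 5.2 as written, although SeraSeal did not control all of its bleeding.

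The headline claim is that SeraSeal controls bleeding by itself in under 5 minutes in 95% of cases, against procedures that historically take more than 6 minutes to bring every hemorrhage under control. A case that standard methods had to finish does not support that claim. The study is unblinded and non-randomized, and the surgeon may decide on the switch. Under 7.1 the monitor's check for completeness and accuracy leaves out the time to hemostasis. These features make it desirable to settle the scoring before any results are seen.

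**Working it through.** **The plan's own figure.** The planned size is 120. For a single proportion with p = 0.5 (assumed; the protocol does not state it), half-width 0.05 and z = 1.96, n0 = 1.96² × 0.25 / 0.05² = 384.1. Corrected for a population of 175, n = 384.1 / (1 + 383.1/175) = 120.4, so 120 is reproduced. Here it serves only as the denominator of the success rate.

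**Which switches can precede 5 minutes.** Each stopping criterion is set against the clock and the 5-minute limit.

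- *Summed time over 5 minutes.* The total is already beyond the limit, so the case fails the primary. No gap.
- *Surgeon's discretion or serious adverse event.* No minimum time applies. Section 5.6 expects hemostasis in 1 to 2 minutes per bleed ("After 1-2 minutes, when hemostasis is achieved"). Two controlled bleeds then take 2 × 1 = 2 to 2 × 2 = 4 minutes. If the switch falls between bleeds, the recorded total is 2 to 4 minutes. If a third bleed is under way and its clock runs on, 5 − 4 = 1 to 5 − 2 = 3 minutes remain for a standard method to finish it within the limit.
- *Three failed applications on one wound.* Let each application be judged after t minutes (assumed; the protocol gives no time to declare failure), and let the standard method need a further s minutes. The total stays under the limit if 3t + s < 5.
  - t = 1: 3 minutes have passed, leaving s < 2.
  - t = 1.5: 4.5 minutes have passed, leaving s < 0.5.
  - t = 5/3 = 1.67 minutes (100 seconds): 5 minutes have passed and the route is closed.
  - t = 2: 6 minutes, so the 5-minute criterion acts first.
  - With one earlier bleed of 1 minute, 3t must be below 4, so t < 1.33 minutes (80 seconds).

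The discretion and adverse-event routes are therefore clearly open. The three-application route is open only with quick judgments.

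**Whether anything scores these cases.** Section 5.6 switches the patient and stops there. Section 6.3 withdraws a patient with an allergic reaction and assigns no outcome. Section 7.2 does not combine breaks with the primary. If the clock runs through the switch, the bleed receives a time that a standard method produced. If it is stopped at the switch, the total is shorter still. Neither reading makes the case a failure.

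**Effect on the rate.** Suppose 114 of 120 cases meet the criterion as written (114/120 = 95.0%, the protocol's expected proportion), and k of those 114 were switched early. Both are assumptions. Scored as non-success, the rate is (114 − k)/120.

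| k | Rate |
|---|---|
| 1 | 113/120 = 94.2% |
| 3 | 111/120 = 92.5% |
| 6 | 108/120 = 90.0% |

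Each case moves the rate by 1/120 = 0.83 points. Six move it by 5 points, which equals the whole failure allowance.

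**The case against.** The best reply is that the intent is plain. Sections 5.1 and 5.2 and the expectation stated in 5.6 all make SeraSeal the agent of the timed event, and 5.5 ties effectiveness to the product. This stands as evidence of intent. It is not a scoring rule, and hemostasis following application is literally met when cautery finishes the bleed.

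A reader might infer that a switch has no bearing at all on the primary. The protocol does not support that. A switch because the total exceeds 5 minutes is a primary failure by definition. The three-application criterion is itself worded as failure to achieve hemostasis, so it can fairly be read as a failure on the endpoint. The clear gap is narrower: discretion and serious adverse events.

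A reader might also infer that bleeds arising after a switch add no time. They have no first application and hence no start, but the protocol does not say how they enter the total. Since the total is meant to cover the whole operation, such a case could equally be called incomplete. The point does not need that inference.

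A statistical analysis plan, not shown here, might add a rule, and breaks are openly reported as a secondary endpoint. Both remarks are fair. However, the endpoint, its clock and the switching rules are fixed in the protocol, and the clock as written can yield a success for a case that standard methods finished. A separate break count does not remove that case from the headline rate.

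**Conclusion.** The point holds in a limited form. The protocol's clock ends when bleeding stops, by whatever means. Three of the four stopping criteria can lead to standard methods before 5 minutes: two without any time restriction, and one only if the three applications together take less than 5 minutes. For these, nothing prevents the case from counting within the 5-minute criterion, contrary to the purpose in 5.1.

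The size per case is certain, at 0.83 points of 120. The total effect is not known. The protocol gives no switch frequency, and the 114/120 starting point, k, t and s are illustrative. It would go too far to say that the protocol declares switched cases successes, or that the reported rate will be inflated by a given amount. What can be said is that, at a result of exactly 95%, one such case decides which side of the target the study falls on. It should be fixed before results are seen.

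**What to change.** State in 5.6 that success on the primary is a summed time under 5 minutes with hemostasis achieved by SeraSeal alone. State also that any case switched to a standard modality to control bleeding, under any stopping criterion, is a non-success. The surgeon's freedom to switch stays as it is.

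The cost is small. The secondary endpoint already requires breaks to be known case by case, so no new data source is needed. Each reclassified case lowers the reported rate by 0.83 points. A switch for an adverse event unrelated to SeraSeal would also count against the product, so report those cases separately. A sensitivity analysis that excludes switched cases, and a note on whether planned ligation of a vessel that is not bleeding counts as a break, are optional additions.

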The patients will be monitored for post-operative bleeding and overall wound healing for those wounds that can be observed. A base line hemoglobin (HGB), hematocrit (HCT), prothrombin time (PT), partial thromboplastin time (PTT) be drawn, and measured at 24 to 48 hours after surgery. The patients will be observed and assessed for a minimum of 48 hours after application of SeraSeal for signs of post-operative bleeding, and hypersensitivity to the investigational product throughout the hospitalization period. They will be assessed for, but not limited to, skin rash; wheezing; anaphylaxis; pruritus; prolong coagulation tests; delayed healing or infection through quantitative cultures. In the event there is progression of edema leading to respiratory distress, anaphylaxis, or shock due to blood loss, a crash cart and/or any additional standard and customary treatment(s), will be available. This study will not limit the standard of care performed at the four investigational hospitals. The following components of wound care are "standard practice" at each of the hospitals: daily dressing changes; quantitative cultures when infection may be present; routine blood tests. All enrolled study subjects may request to be withdrawn from the study at any time, and will be terminated from the study and provided standard of care. All adverse events will be recorded according to whether the event was unrelated, unlikely, possibly or probably related to the study treatment.

Table 1: Schedule of Assessments

Test	Pre-Op	Surgery	4-8 Hrs Post-Op	24-48 Hrs Post-Op
Informed Consent	X			
History		X		
Physical Examination	X		X	X
HGB	X		X ⁺	X [#]
HCT	X		X ⁺	X [#]
PT	X		X ⁺	X [#]
PTT	X		X ⁺	X [#]
ECG	X		X ⁺	X [#]
Radiological work-up	X		X ⁺	X [#]
Adverse Events		X	X	X [#]
Effectiveness		X	X	X
Safety		X	X	X

+ measured as often as needed.

monitored beyond 48 hours and as needed

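### The primary time to hemostasis ends at the first sight of no bleeding, with no check after excess product is removed and no rule for re-bleeding, so momentary control can be scored as success

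*Protocol*

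**What the plan says.** All references are to the protocol.

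- **Endpoint.** Section 5.6: "The primary endpoint in this clinical trial is hemostasis". Section 7.2 names time to hemostasis as the primary outcome. Section 5.2 sets the target as a collective time under 5 minutes in 95% of cases.
- **Clock.** Section 5.6: "A time to hemostasis is measured from the time when the product is first applied to the wound, until no bleeding or oozing is observed". The only stopping condition is that the clock runs "until no bleeding or oozing is observed from the wound".
- **Removal of excess.** Section 5.6: "After 1-2 minutes, when hemostasis is achieved, the excess SeraSeal will either be removed through suction or absorption onto a surgical sponge". No inspection after this step is described.
- **Summation.** Section 5.6: "the time to hemostasis for each bleed will be measured, then totaled for the entire surgery".
- **Limits on treatment.** Section 5.6 moves the patient to standard practice if "hemostasis fails to be achieved after 3 applications for a particular wound, the collective time to hemostasis exceeds 5 minutes". A serious adverse event or the surgeon's judgement can also trigger the move.
- **Effectiveness and safety.** Section 5.5 (What this study will determine) bases effectiveness on reaching hemostasis after application. It lists "recurrence of bleeding, infection, lack of healing, and presence of hypersensitivity reactions" as the outcomes that determine safety.
- **Follow-up.** Section 5.6 has patients "observed and assessed for a minimum of 48 hours after application of SeraSeal for signs of post-operative bleeding". Table 1 marks an Effectiveness row at 4-8 and 24-48 hours after surgery but does not say what is assessed there.

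**The concern.** Section 5.1 has SeraSeal used alone from first incision to closing. A claim of that kind needs control that lasts at least until the wound is closed, and in practice beyond. The primary measurement asks only whether there was a moment at which no bleeding was seen.

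Three gaps follow:

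1. That moment needs no minimum duration and no confirmation after the excess has been suctioned or sponged away.
2. It is not stated how a wound that was declared dry and then bleeds again before closing enters the total.
3. Bleeding found after surgery has no stated route to the 5-minute result.

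For the absolute claim in Section 5.2, counting a momentary stop as success can only raise the SeraSeal rate. The study is unblinded, and Section 7.1 exempts time to hemostasis from the monitor's check of completeness and accuracy, so a loose stopping point would be hard to detect later.

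An analysis plan cannot repair the first gap. The stopwatch rule is a bedside measurement, and an observation after removal that was never made cannot be derived afterwards.

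**Working it through.** **Step 1. Order of events for one wound (Section 5.6).** Product is applied and the clock starts. No bleeding or oozing is seen and the clock stops. The excess is removed when hemostasis is achieved. The last event therefore follows the one that stops the clock, and nothing after it is timed unless bleeding is recorded as something new.

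**Step 2. Re-bleed at a treated wound before closing.** Let T be the case total without the re-bleed, with T under 5 minutes, and let t be the time needed to control the re-bleed. Three readings fit the text:

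| Reading | Case total |
|---|---|
| The re-bleed is a new bleed with its own clock | T + t |
| The wound's clock re-opens from first application | T + t + the dry interval between |
| The wound has already reached its endpoint and is not timed again | T |

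If T + t is 5 minutes or more, the first two readings give a failure and the third a success. The summation rule favours the first reading, and the definition of the clock's start allows the second. The protocol does not choose.

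**Step 3. Re-bleed after surgery.** Section 5.5 puts recurrence under safety. Table 1 lists Effectiveness after surgery without content. No sentence lets either alter the case's total, so as written a case that re-bleeds at the 4-8 hour assessment can keep its result of under 5 minutes.

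**Step 4. The plan's own figures.** Section 7.2 gives 120 patients from 175 cases, 95% confidence and an interval of 5. With z = 1.96, p = 0.5 and d = 0.05:

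- n0 = z² p(1 − p)/d² = 1.96² × 0.25/0.05² = 384.1
- n = n0/(1 + (n0 − 1)/175) = 384.1/(1 + 383.1/175) = 120.4

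The stated 120 reproduces. It is used here only as a denominator: 95% of 120 is 114 cases.

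**Step 5. Illustration of size.** The protocol gives no re-bleed rate. Let r be the assumed share of initial successes that re-bleed. Sustained success is S = 0.95 × (1 − r). The last column is the binomial probability of at least 114 sustained successes among 120 when the true rate is S.

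| r (assumed) | S | Expected sustained successes, 120 × S | Successes lost, 114 × r | P(at least 114 of 120) |
|---|---|---|---|---|
| 0% | 95.0% | 114.0 | 0 | 0.61 |
| 1% | 94.1% | 112.9 | 1.1 | 0.42 |
| 2% | 93.1% | 111.7 | 2.3 | 0.27 |
| 5% | 90.3% | 108.3 | 5.7 | 0.046 |
| 10% | 85.5% | 102.6 | 11.4 | 0.0008 |

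The threshold of 114 is simply the 95% target applied to 120 patients. The protocol states no decision rule in that form.

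**The case against.** A reader might infer that re-bleeding never counts against the primary result. The document does not support that. Section 5.6 times every bleed and sums over the whole operation, and it limits both applications per wound and total time. A wound that re-bleeds before closing can quite naturally be read as another bleed that adds to the total. A change to a standard method would also count against the secondary endpoint of cases without a therapeutic break. The undefined Effectiveness row in Table 1 likewise rules out a flat statement that later findings are ignored. What remains is that the rule is unstated, not that re-bleeding is excluded.

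A reader might also infer that liquid product hides bleeding, or that removing it dislodges the clot. The protocol says neither, and the point does not need them. It needs only that removal comes after the clock stops and that no recheck is described.

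Three further objections have weight:

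- **Separate reporting is legitimate.** Timing initial control and reporting recurrence as a safety outcome is an accepted design, and recurrence is followed here for at least 48 hours.
- **The benchmark.** The historical cases are described only as taking more than 6 minutes to control all hemorrhages. Nothing says that this required lasting control. If it measured initial control, demanding durability of SeraSeal alone would make the comparison less like-for-like. A bias in favour of SeraSeal is therefore clear for the 95% claim but not shown for the historical comparison.
- **Ascertainment.** Section 5.6 limits post-operative monitoring to wounds that can be observed. Section 5.7 lists patients on anticoagulants or with blood disorders under inclusion, so late bleeding may be hard to see or to attribute to failed initial control.

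These are good reasons not to make freedom from bleeding at 24-48 hours part of the primary endpoint. They do not answer the missing check after removal or the missing timing rule before closing.

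**Conclusion.** The point holds in a limited form. As written, the primary measurement requires neither a bleeding-free interval nor confirmation after the excess is removed. It leaves the timing of a re-bleed at a treated wound open and states no link between recurrence and the 5-minute result. Momentary control can therefore be scored as success. It does not follow that it always is, or that re-bleeding during surgery is ignored.

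The size cannot be taken from the document. The fall from 95% to 93.1%, 90.3% or 85.5% rests wholly on assumed re-bleed rates of 2%, 5% and 10% among initial successes, and on an initial success rate exactly at the target. Because the target is itself 95%, there is no margin under that assumption: even a 2% rate puts sustained success below it. The correction should be made because it is cheap and specific, not because a large effect has been shown.

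**What to change.** 1. In Section 5.6, count a bleed as controlled only if absence of bleeding or oozing is confirmed after the excess product has been removed.
2. State that the time of any re-bleed at a treated wound before closing is added to that case's total, and say when timing of a re-bleed starts.
3. Keep the 5-minute total as the primary outcome. Report beside it, as a pre-specified supportive result, the proportion of cases that meet it and have no recorded re-bleeding at a treated site through the 24-48 hour assessment already in Table 1. Note that this covers only wounds that can be observed.
4. Say what the Effectiveness row of Table 1 records after surgery.

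The collective time and the count of applications also serve as criteria for stopping treatment. The protocol should state whether the revised timing applies to those criteria too. That is for the sponsor and the investigators to reconcile, and nothing is proposed here about the limits themselves.

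**Cost.** The change needs revised endpoint wording, one confirmatory observation per bleed, a field on the surgery form for re-bleeds, and one derived variable from a visit already scheduled. Recorded times will be slightly longer and the success rate somewhat lower. If the 6-minute historical benchmark measured initial control only, some like-for-like comparability may be lost, and the report should say so.
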